## Appendix 2 Pharmacokinetic, Immunogenicity, and Pharmacodynamic Biomarkers Blood Sampling Schedule

Cycle	Day	PK 	ADA	PBMC Flow Cytometry	PBMC T Cell Repertoire
Screening	Screen			Screening 	
	1	Pre infusion	Pre Infusion	Pre Infusion	Pre Infusion
	7-14	Only done ONCE on Days 7-14, the first time the patient reaches 500 ng/kg/day dose level		Only done on Day 8	
		One sample at least 1 hour after 500 ng/kg/day dose level reached		Sample may be drawn at any time relative to infusion	
Cycle 1	15	
 
Patient reached 500 ng/kg/day dose level before Day 15: Sample may be drawn at any time relative to infusion
 
Patient reaches 500 ng/kg/day dose level on Day 15: Sample at least 1 hour after 500 ng/kg/day dose level reached
 
		Sample may be drawn at any time relative to infusion	
	22	
 
Patient reached 500 ng/kg/day dose level before Day 22: Sample may be drawn at any time relative to infusion
 
Patient reaches 500 ng/kg/day dose level on Day 22: Sample at least 1 hour after 500 ng/kg/day dose level reached
 
		Sample may be drawn at any time relative to infusion	
	25	Patient reached 500 ng/kg/day dose level before Day 25:         Sample may be drawn at any time relative to infusion         Patient reaches 500 ng/kg/day dose level on Day 25:         Sample at least 1 hour after 500 ng/kg/day dose level reached         Immediately prior to end of infusion 3		Sample may be drawn at any time relative to infusion	Sample may be drawn at any time relative to infusion
	29	minediatery prior to end or musion 			

Cycle	Day	PK 	ADA	PBMC Flow Cytometry	PBMC T Cell Repertoire
			Sample may be	Sample may be	Sample may be
$Cycles \geq 2$	1	Sample may be drawn at any time relative to infusion	drawn at any time	drawn at any time	drawn at any time
			relative to infusion	relative to infusion	relative to infusion
			28-days following	28-days following	28-days following
End of	n /2	28-days following last treatment or	last treatment or	last treatment or	last treatment or
Treatment	n/a	at time of treatment failure	at time of treatment	at time of treatment	at time of treatment
			failure	failure	failure

Abbreviations: ADA = anti-drug antibody; PBMC = peripheral blood mononuclear cell; PK = pharmacokinetics.

1 For patients who will discontinue therapy, a PK sample is to be collected at end of infusion. When dosing is delayed for ≥ 24 hours, PK samples should not be collected on days when no study drug is administered. After Cycle 1 Day 1, PK samples do not need to be collected if patient does not reach 500 ng/kg/day dose level.

2 Sample may be drawn up to Day -5.

3 Cycle 1 Day 29 PK samples are only to be collected if there is a > 24 hour interruption in treatment between Cycles 1 and 2.

## Appendix 3International Working Group (IWG) Response Criteria for Acute Myeloid Leukemia
(AML) Modified for Assessment of AML in this Study

Response Criterion	Time of Assessment	Neutrophils* (µL)	Platelets* (μL)	Bone Marrow Blasts (%)	Other
Complete Remission (CR)	Day 25 + 3 days (each cycle)	≥ 1,000	≥ 100,000	< 5	Transfusion # Extramedullary disease (EMD)
• Morphologic CR (mCR)	Day 25 + 3 days (each cycle)	$> 1,000 \ge 100,000 < 5$		Transfusion # EMD	
• Cytogenetic CR (CRc)	Day 25 + 3 days (each cycle)	≥1,000	≥ 100,000	< 5	Cytogenetics – normal, EMD
• Molecular CR (CRm)	Day 25 + 3 days (each cycle)	≥1,000	≥ 100,000	< 5	Molecular – negative, EMD
CR with partial hematologic recovery (CRh)	Day 25 + 3 days (each cycle)	≥ 500	≥ 50,000	< 5	Transfusion \$ EMD
CR with incomplete blood count recovery (CRi)	Day 25 + 3 days (each cycle)	< 1,000	< 100,000	< 5	Transfusion \$ EMD
CR with incomplete neutrophil recovery (CRn)	Day 25 + 3 days (each cycle)	< 1,000	≥ 100,000	< 5	Transfusion § EMD
• CR with incomplete platelet recovery (CRp)	Day 25 + 3 days (each cycle)	≥ 1,000	< 100,000	< 5	Transfusion \$ EMD
Morphologic leukemia-free state (MLFS)	Day 25 + 3 days (each cycle)	NA	NA	< 5	EMD
Partial remission (PR)	Day 25 + 3 days (each cycle)	> 1,000	> 100,000	> 50% decrease or decrease to 5-25	Blasts < 5% if Auer rod positive
Other benefit (OB)	Day 25 + 3 days (each cycle)	NA	NA	> 30% decrease	NA
Stable disease (SD)	Day 25 + 3 days (each cycle)	NA	NA	Absence of CR, CRh, CRi, PR, MLFS, OB, and criteria for PD not met	NA

Response Criterion	Time of Assessment	Neutrophils* (µL)	Platelets* (μL)	Bone Marrow Blasts (%)	Other		
Progressive disease	NA	NA	NA	
 
Evidence for an increase in bone marrow blast percentage and/or increase of absolute blast counts in the blood:
 
> 50% increase in marrow blasts over baseline (a minimum 15% point increase is required in cases with < 30% blasts at baseline; or persistent marrow blast percentage of > 70% over at least 3 mo; without at least a 100% improvement in ANC to an absolute level (>0.5 x 10^9/L [500/mL], and/or platelet count to >50 x 10^9/L [50 000/mL] non-transfused); or
 
> 50% increase in peripheral blasts (WBC x % blasts) to > 25 x 10^9/L (> 25 000/mL) (in the absence of differentiation syndrome)†; or
 
New extramedullary disease
 
	In general, at least 2 cycles of flotetuzumab should be administered to determine "progressive disease". "Progressive disease" is usually accompanied by a decline in ANC and platelets, increased transfusion requirement, and decline in performance status or increase in symptoms		
Recurrence/relapse	Relapse after CR is defined as a reappearance of leukemic blasts in the peripheral blood and $\geq$ 5% blasts in the bone marrow not attributable to any other cause (e.g., bone marrow regeneration after consolidation therapy)						

CR = complete remission (includes mCR, CRc, CRm).

 $CRi = includes neutrophil count \ge 1000 \text{ or platelet count} \ge 100,000.$ 

\*Assessment is quantitated by BM biopsy and best CBC (up to 14 days post BM biopsy).

# No RBC and/or platelet transfusion within 5 days prior to response assessment.

§ No platelet transfusion within 5 days prior to response assessment

† Certain targeted therapies, for example, those inhibiting mutant IDH proteins, may cause a differentiation syndrome, that is, a transient increase in the percentage of bone marrow blasts and an absolute increase in blood blasts; in the setting of therapy with such compounds, an increase in blasts may not necessarily indicate PD.

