#### **Bone Marrow Aspirate and Biopsy**

### • Responders (CR, CRh, CRi [CRn, CRp], or MLFS):

Patients who respond to treatment should have a bone marrow aspirate and biopsy collection at 3 and 6 months post treatment at the study site. After 6 months post treatment, bone marrow aspirate and/or biopsy will be performed per standard of care.

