# 9.6.2.1 Key Secondary Efficacy Analyses

The key secondary efficacy endpoints include CR rate, CRh rate, duration of response, postbaseline transfusion independence rate, HSCT rate, and incidence and duration of hospitalization.

**Duration of response (DOR)** will be calculated from the time of initial documentation of response to the time of disease relapse or death due to any cause, whichever occurs first. Patients who are still in response at study completion without alternative therapies will be censored at the time of their last disease assessment. Duration of response will be calculated

for patients who achieve the first evidence of CR or CRh as primary analysis. A separate exploratory analysis will be conducted for patients who achieve the first evidence of overall complete response (CR, CRh, CRi [CRn, CRp], or MLFS).

**Post-baseline transfusion independence** is defined as no transfusion during any consecutive 56-day period on-study. Post-baseline transfusion independence will be summarized for RBC and platelet transfusion separately and in total. Transfusion dependence at baseline is defined as any red blood cell or platelet transfusions during the 28 days prior to the first dose of study drug. The rate of conversion from transfusion dependence to transfusion independence will be calculated. The rate of patients who are transfusion independent at baseline and remain independent during any 56-day post-baseline period will also be calculated.

**HSCT rate** is defined as rate of successful HSCT through study treatment. Patients who received other therapies (except for conditioning therapy) for AML after discontinuation of study drug and later undergo a subsequent HSCT will not be included. Number and percentage of patients with HSCT will be summarized.

**Incidence and Duration of Hospitalization,** summaries will be provided for the efficacy population, as well as independently for patients who achieved CR or CRh. Summaries will include duration of initial hospitalization as well as incidence, number and duration of subsequent hospitalizations following the initial discharge, number of days hospitalized, and the reasons for hospitalization.

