# 9.6.2.2 Additional Secondary Efficacy Analyses

Additional secondary efficacy endpoints include overall complete response rate, objective response rate, subgroup analyses of CR/CRh, CR, CRh and overall complete response rates, overall survival, event-free survival, time to response, mortality rate at 30, 60, 90, and 180 days, six-month and one-year survival.

**Overall complete response rate (OCRR)** is defined as the rate of CR+CRh+CRi [CRn, CRp]+MLFS according to IWG AML response criteria (**Appendix 3**), and includes any response which achieves < 5% BM blasts by morphology.

**Objective response rate** is defined as the rate of CR+CRh+CRi [CRn, CRp]+MLFS+PR according to IWG AML response criteria (**Appendix 3**).

Subgroup analyses of CR/CRh, CR, CRh, and overall complete response rates will be performed by baseline disease characteristic (e.g., age group [ $< 70, \ge 70$ ], gender, cytogenetic risk status [high, intermediate, low], prior line of therapy [1, 2, 3], TP53 gene mutations).

**Overall survival** is defined as the time between the date of the first dose of study drug and death from any cause. Patients who are alive or whose death status is unknown will be censored at the last date known to be alive on or before the data cutoff date.

**Event-free survival** is defined as the time from the first dose of study drug until date of relapse from CR, CRh, or CRi (CRn, CRp), or death from any cause, whichever occurs first.

Patients who are not known to have any of these events at study completion will be censored at the date of the last disease assessment.

**Time to response** (TTR) is defined as time from first dose of study drug to first CR, CRh, CRi (CRn, CRp), or MLFS, and will be summarized with descriptive statistics. Time to CR/CRh and time to best overall response will be calculated.

**Mortality rate** is defined as rate of death from any cause within 30, 60, 90, or 180 days of first dose of study drug.

**Six-month survival rate** is defined as the probability of survival at 6 months from first dose of study drug.

**One-year survival rate** is defined as the probability of survival at 1 year from first dose of study drug.

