11.2.1 Key Secondary Efficacy Analyses

The key secondary efficacy endpoints include CR rate, CRh rate, duration of response, postbaseline transfusion independence rate, HSCT rate and incidence and duration of hospitalization.

Duration of response (DOR) will be calculated from the time of initial documentation of response to the time of disease relapse or death due to any cause, whichever occurs first. Patients who are still in response at study completion without alternative therapies will be censored at the time of their last disease assessment.

Duration of response will be calculated for patients who achieve the first evidence of CR or CRh as primary analysis. A separate exploratory analysis will be conducted for patients who achieve the first evidence of complete response (CR, CRh, CRi [CRn, CRp], or MLFS).

DOR (months) = (date of event [disease relapse or death] or date of censoring –date of first evidence of response + 1) / (365.25/12)

Sensitivity analyses will be done for duration of response by using the additional censoring rules below:

- Censored at the date of HSCT.
- Censored at the date of other alternative therapies such as surgery, procedure, radiation and subsequent antileukemic therapy, etc.
- Patients with two or more consecutive missing response assessments prior to event will be censored at the last date of response assessment before the missing assessments.

The duration of response will be analyzed using the KM method. The 25th percentile, median and 75th percentile time (including two-sided 95% CI) will be summarized.

Post-baseline transfusion independence is defined as no transfusion during any consecutive 56-day period on-study. Post-baseline transfusion independence will be summarized for RBC and platelet transfusion separately and in total. Transfusion dependence at baseline is defined as any red blood cell or platelet transfusions during the 28 days prior to the first dose of study drug. The rate of conversion from transfusion dependence to transfusion independence will be calculated. The rate of patients who are transfusion independent at baseline and remain independent during any 56-day post-baseline period will also be calculated.

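### The only relapse rule applies after CR and needs blasts in both blood and marrow, so DOR and responder EFS can miss or postdate a marrow-only recurrence

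*Protocol*

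**What the plan says.** **Relapse row.** Protocol Appendix 3 and SAP Appendix 1 share one row: "Relapse after CR is defined as a reappearance of leukemic blasts in the peripheral blood and" at least 5% marrow blasts with no other explanation, marrow regeneration being the example given. The footnote in both reads "CR = complete remission (includes mCR, CRc, CRm". The abbreviation lists of both documents give CR the same three components, and CRh, CRi and MLFS have rows of their own.

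**DOR.** This is a key secondary endpoint. It runs from first documented response to relapse or death and is calculated "for patients who achieve the first evidence of CR or CRh as primary analysis" (Protocol 9.6.2.1; the same in SAP 11.2.1). An exploratory analysis adds CRi and MLFS.

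**EFS.** This is an additional secondary endpoint. It runs from "first dose of study drug until date of relapse from CR, CRh, or CRi (CRn, CRp), or death from any cause" (Protocol 9.6.2.2; likewise Protocol 7.10, SAP Table 4 and SAP 11.2.2).

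**Follow-up.** Protocol 8.3.2 and Appendix 1 schedule, for responders, "bone marrow aspirate and biopsy collection at 3 and 6 months post treatment".

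**The concern.** The relapse row decides when a response is recorded as lost, and it does not fit the endpoints that use it. Every remission row requires marrow blasts below 5%, so a marrow of 5% or more ends remission by the appendix's own standard. The relapse row waits for blasts in the blood as well. It also names only CR, while DOR and EFS need a rule for CRh and CRi.

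DOR is reported beside the CR/CRh rate in a single-arm pivotal cohort, with no control arm to carry the same distortion. If the event rule postdates loss of remission, the response looks more durable than it was. Two analysts could also date the same recurrence differently.

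**Working it through.** **1. The plan's own figures.** The documents state no sample size, power or precision for DOR or EFS. The only stated operating characteristics belong to the CR/CRh design. Inputs (Protocol 9.1, SAP 4.2): looks at 40, 100 and 170; continue at 5 or more and 15 or more responses; success at 25/100 or 35/170; rates 14.7% and 23%. An exact three-stage binomial calculation gives:

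| Quantity | Stated | Recomputed |
|---|---|---|
| Alpha at second interim | 0.005 | 0.0047 |
| Overall alpha | 0.024 | 0.0239 |
| Power | about 80% | 0.787 |
| Early termination under H0 | 55% | 0.546 |

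Relapse enters none of these, so they do not change.

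**2. Endpoints against the relapse row.**

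| Endpoint | States from which relapse must be defined | State named in the relapse row |
|---|---|---|
| DOR, primary | CR, CRh | CR |
| DOR, exploratory | CR, CRh, CRi, MLFS | CR |
| EFS | CR, CRh, CRi | CR |

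**3. One patient through the appendix.** Take a patient in CR whose 3-month marrow shows 15% blasts, with clear blood and no extramedullary disease (illustrative values).

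- Remission rows: all need marrow below 5%. Not met.
- Relapse row: the marrow element is met, the blood element is not. Not relapse.
- Partial remission row: its marrow entry includes "50% decrease or decrease to 5-25". If counts exceed that row's thresholds, the recurrence literally fits partial remission, which is not an event.
- Progressive disease row: its marrow-increase criterion is relative to baseline ("50% increase in marrow blasts over baseline (a minimum 15% point increase is required in cases with" low baseline blasts). Whether it is met does not matter here, because neither DOR nor EFS counts progression.

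So there is no DOR or EFS event on that date. If the finding were new extramedullary disease alone, it would fall under progression only, and again no event would be recorded. If the patient had been in CRh, the relapse row would not strictly apply even with blasts in both blood and marrow.

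**4. Direction.** Let M be the time marrow blasts reach 5%, B the time blood blasts reappear, X the time of new extramedullary disease and D death.

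- As written: event time = min(max(M, B), D).
- Dated at first evidence of recurrence: event time = min(M, B, X, D).

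Since max(M, B) ≥ min(M, B, X), the recorded time is never shorter under the written rule. It is longer whenever the signs do not appear together and death does not come first. Censoring the patient instead also removes the event at M.

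**5. Number of patients.** At the target, 0.23 × 170 = 39.1, so about 39 patients form the primary DOR set; at the final success boundary it is 35. These are ceilings on the number affected. Patients in CR who die in remission, or whose recurrence appears in blood and marrow together, are recorded correctly. EFS adds patients in CRi, whose number the documents do not give.

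**6. Size of the bias.** This needs the share of recurrences first seen in marrow alone or outside the marrow, and the lag to blood blasts. Neither document gives these, so no figure in months can be derived.

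**The case against.** **The text implies one relapse rule for CR, CRh and CRi.** All four EFS definitions name these states together. This stands as evidence of intent: a reader might infer that the plan has no concept of relapse from CRh or CRi, and that goes too far. The defect is that the row supplying the criteria was not aligned with the endpoints. The footnote says that CR includes three subtypes, which could be read loosely, but the abbreviation lists and the separate rows leave no real room for CRh or CRi.

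**The joining word may be meant loosely.** Possibly, and the exemption for marrow regeneration shows that marrow blasts were meant to be judged by cause. But nothing in either document relaxes the conjunction.

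**The case is unspecified, not lengthened.** DOR censoring applies to patients still in response, and a patient with 15% marrow blasts is not. That is fair: neither the event rule nor the censoring rule plainly fits. Still, no literal reading puts an event at the marrow finding. The SAP's DOR and EFS sensitivity analyses only add censoring, so they do not repair this.

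**EFS should count treatment failure.** A reader might infer a second error here. The documents do not support that. EFS is relapse or death in all four places and is descriptive. Protocol 4.1 also gives a reason for caution: 3 of 21 CR patients responded after an initial blast increase following Cycle 1. Counting failure would be a redefinition needing several exceptions.

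**The cutoff wording is faulty.** DOR and EFS refer to study completion, while OS refers to the data cutoff. Protocol 4.4 and 8.3.2 also describe the end of follow-up differently. These need aligning, but the censoring date itself, the last disease assessment, is stated.

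**Conclusion.** The point holds for the relapse rule. As written, both appendices give no DOR or EFS event at a marrow-only recurrence or at new extramedullary disease, and the row does not name CRh, CRi or MLFS. The consequence is missed or delayed events, so DOR, and EFS among responders, is overstated. This rests on the literal wording and assumes that some recurrences appear first in marrow or outside it.

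At most about 39 of 170 patients in the primary DOR set depend on the rule at the 23% target. The size of the bias is unknown. A reader might infer that such a recurrence is never counted; in fact it becomes an event once blood blasts appear or the patient dies. A reader might also try to size the problem from the gap between the remission and progression thresholds, but that gap says nothing about endpoints that do not count progression.

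The correction should be made because DOR is a key secondary endpoint. The primary CR/CRh analysis, alpha, power and N=170 are untouched.

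**What to change.** In Protocol Appendix 3 and SAP Appendix 1, add a relapse definition **for DOR and EFS analysis only, with no change to treatment decisions**. After CR, CRh or CRi (and after MLFS for the exploratory DOR), relapse is any one of:

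- reappearance of leukemic blasts in the blood;
- marrow blasts of 5% or more not attributable to another cause;
- new extramedullary disease.

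Date it at the first assessment that shows it. Refer to this definition from Protocol 7.10 and 9.6.2 and from SAP 11.2.1 and 11.2.2.

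The cost is a wording amendment in both documents. It needs no new visits, because responder marrows and disease status are already collected. Reported DOR and EFS may be slightly shorter.

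Optional clarifications, separate from the error:

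- report a supplementary EFS that counts documented treatment failure, or label the present endpoint relapse-or-death;
- tie study completion to the data cutoff for DOR and EFS;
- reconcile the end-of-trial text (Synopsis and Protocol 4.4) with the follow-up text in Protocol 8.3.2.

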Appendix 1 International Working Group (IWG) Response Criteria for Acute Myeloid Leukemia (AML) Modified for Assessment of AML in this Study

AE	adverse event
AESI	adverse event of special interest
AML	acute myeloid leukemia
CR	complete remission (mCR, CRc, or CRm)
CR1	initial CR
CRc	cytogenetic complete remission
CRh	complete remission with partial hematologic recovery
CRi	complete remission with incomplete blood cell recovery
CRm	molecular complete remission
CRn	CR with incomplete neutrophil recovery
CRp	CR with incomplete platelet recovery
CRS	cytokine release syndrome
CTCAE	common terminology criteria for adverse events
DLT	dose-limiting toxicity
DOR	duration of response
DSM	Data Safety Monitor
EBV	Epstein-Barr Virus
ECG	electrocardiogram
ECOG	Eastern Cooperative Oncology Group
eCRF	electronic case report form
EFS	event-free survival
EOTV	end of treatment visit
ER	early relapse
FDA	Food and Drug Administration
HSCT	hematopoietic stem cell transplantation
IDMC	independent data monitoring committee
IRR	infusion related reaction
IWG	International Working Group
mCR	morphologic CR
MLFS	morphologic leukemia-free state
MRD	minimal residual disease
MTD	maximum tolerated dose
MTDS	maximum tolerated dose and schedule
OS	overall survival
PBMC	peripheral blood mononuclear cell
PD	progressive disease

LIST OF ABBREVIATIONS

PIF	PIF primary induction failure	
PK pharmacokinetics		
PR partial remission		
SAE serious adverse event		
SD stable disease		
SPP statistical programming plan		
TLFs tables, listings and figures		
TTR time to response		
WBC white blood cell (count)		

1 INTRODUCTION

Flotetuzumab (MGD006) is a CD123 x CD3 DART protein developed by MacroGenics, Inc., designed to target CD123-positive cells (including AML cells) for recognition and elimination by CD3-expressing T lymphocytes as effector cells.

This statistical analysis plan (SAP) provides a detailed and comprehensive description of the analysis of the study CP-MGD006-01 entitled "A Phase 1/2, First-in-Human, Dose Escalation Study of MGD006, a CD123 x CD3 Dual Affinity Re-Targeting (DART) Bi-Specific Antibody-Based Molecule, in Patients with Relapsed or Refractory Acute Myeloid Leukemia or Intermediate-2/High Risk Myelodysplastic Syndrome".

